5.1 Study treatment

5.1.1 Investigational and control drugs

All eligible patients will be randomized 1:1 to either LCZ696 titrated to a target dose of 200 mg twice daily or ramipril titrated to a target dose of 5 mg twice daily in a double-blind manner for the duration of the study. In addition, patients will continue to receive optimal standard of care background therapy to treat the index MI event and co-morbid conditions, as considered appropriate by the investigator and in accordance with the local/institutional guidelines, with the exception of an ACE inhibitor or ARB as this will be replaced by study drug. The use of an open label ACE inhibitor or an ARB in addition to randomized study drug is strictly prohibited.

The following study drugs will be provided:

- LCZ696 50 mg, 100 mg and 200 mg tablets, and matching placebo (LCZ696 doses are equivalent to sacubitril/valsartan 24/26 mg, 49/51 mg and 97/103 mg, respectively)
- Ramipril 1.25 mg, 2.5 mg, and 5 mg capsules, and matching placebo
- Valsartan (VAL489) 40 mg and 80 mg tablets, and matching placebo (two doses for 1 day in a subset of randomized patients) ([Section 3.1](#))

All study medications will be supplied in bottles or blister cards. Sufficient medication will be provided for the treatment according to study protocol, including additional medication to allow for delayed visits. Medication labels will be in the local language and comply with the legal requirements of the country. They will include storage conditions for the drug and the medication number, but no information about the patient.

5.1.2 Additional treatment

No additional treatment beyond investigational drug and control drug are included in this trial.

5.2 Treatment arms

Patients will be assigned to one of the following two treatment arms in a ratio of 1:1 at Visit 101.

- LCZ696 at dose levels 1-3 (50, 100 and 200 mg twice daily)
- Ramipril at dose levels 1-3 (1.25, 2.5 and 5 mg twice daily)

5.3 Treatment assignment and randomization

At Visit 101 all eligible patients will be randomized via Interactive Response Technology (IRT) to one of the treatment arms. The investigator or his/her delegate will contact the IRT after confirming that the patient fulfills all the inclusion/exclusion criteria. The IRT will assign a randomization number to the patient, which will be used to link the patient to a treatment arm and will specify a unique medication number for the first package of study drug to be dispensed to the patient. The randomization number will not be communicated to the caller.

The randomization numbers will be generated using the following procedure to ensure that treatment assignment is unbiased and concealed from patients and investigator staff. A patient randomization list will be produced by the IRT provider using a validated system that automates the random assignment of patient numbers to randomization numbers. These randomization numbers are linked to the different treatment arms, which in turn are linked to medication numbers. A separate medication list will be produced by or under the responsibility of Novartis Drug Supply Management using a validated system that automates the random assignment of medication numbers to packs containing the investigational drug(s).

Randomization will be stratified by region and type of index MI (STEMI or NSTEMI).

The randomization scheme for patients will be reviewed and approved by a member of the Novartis Randomization Group.

5.4 Treatment blinding

Patients, investigator staff, persons performing the assessments, and data analysts will remain blind to the identity of the treatment from the time of randomization until database lock, using the following methods:

- Randomization data are kept strictly confidential until the time of unblinding, and will not be accessible by anyone involved in the study with the following exceptions:
 1. The independent and unblinded statistician, programmer and data personnel who are involved in preparing safety and efficacy interim analysis reports for the Data Monitoring Committee (DMC). These personnel will not be involved in any other trial conduct related activities.
 2. DMC members.

- The identity of the treatments will be concealed by the use of investigational treatment that are all identical in packaging, labeling, schedule of administration, appearance, taste and odor.
- A double-dummy design is used because the identity of the study drug cannot be disguised, as the drug products are visibly different.

Unblinding will only occur in the case of patient emergencies (see Section 5.5.9), at the time of an interim analysis by the DMC and at the conclusion of the study.

For any patient whose treatment code has been broken the patient must permanently discontinue the study treatment.

5.5 Treating the patient

Sponsor qualified medical personnel will be readily available to advise on trial related medical questions or problems.

5.5.1 Patient numbering,

Each patient is uniquely identified in the study by a combination of his/her center number and patient number. The center number is assigned by Novartis to the investigative site.

Upon signing the informed consent form, the patient is assigned a patient number by the investigator. At each site, the first patient is assigned patient number ■, and subsequent patients/subjects are assigned consecutive numbers (e.g. the second patient is assigned patient number ■, the third patient is assigned patient number ■). The investigator or his/her staff will contact the IRT and provide the requested identifying information for the patient to register them into the IRT. For studies using eCRFs, only the assigned patient number must be entered in the field labeled "Patient ID" on the electronic data capture (EDC) data entry screen (e.g. enter ■■■■■, etc.). Once assigned to a patient, the patient number will not be reused.

If the patient fails to be randomized for any reason, the IRT must be notified within 2 days that the patient was not randomized. The reason for not being randomized will be entered on the Screening Log, and the screening eCRFs should also be completed.

5.5.2 Dispensing the study drug

Each study site will be supplied with study drug in packaging of identical appearance.

The study drug packaging has a 2-part label. A unique medication number is printed on each part of this label which corresponds to one of the two treatment arms. Investigator staff will identify the study drug package(s) to dispense to the patient by contacting the IRT and obtaining the medication number(s). Immediately before dispensing the package to the patient, investigator staff will detach the outer part of the label from the packaging and affix it to the source document (Drug Label Form) for that patient's unique subject number.

5.5.3 Handling of study and additional treatment

5.5.3.1 Handling of study treatment

Study treatment must be received by a designated person at the study site, handled and stored safely and properly, and kept in a secured location to which only the investigator and designees have access. Upon receipt, all study treatment must be stored according to the instructions specified on the labels. Clinical supplies are to be dispensed only in accordance with the protocol. Technical complaints are to be reported to the respective Novartis country pharma organization (CPO) Quality Assurance.

Medication labels will be in the local language and comply with the legal requirements of each country. They will include storage conditions for the study treatment but no information about the patient except for the medication number.

The investigator must maintain an accurate record of the shipment and dispensing of study treatment in a drug accountability log. Monitoring of drug accountability will be performed by monitors during site visits or remotely and at the completion of the trial. Patients will be asked to return all unused study treatment and packaging at each study visit or at the time of discontinuation of study treatment.

At the conclusion of the study, and as appropriate during the course of the study, the investigator will return all unused study treatment, packaging, drug labels, and a copy of the completed drug accountability log to the Novartis monitor or to the Novartis address provided in the investigator folder at each site.

5.5.3.2 Handling of additional treatment

Not applicable.

5.5.4 Instructions for prescribing and taking study treatment

Novartis will supply the investigators with all study medications required for the course of the study. Patients will be provided with medication packs containing study drug corresponding to their assigned treatment arm and dose level, sufficient to last until the next scheduled visit. In order to adequately blind the study, patients will be required to take a total of two pills, (one tablet from the LCZ696/LCZ696 matching placebo pack and one capsule from the ramipril/ramipril matching placebo pack) twice a day for the duration of the study.

For patients randomized to LCZ696 who were previously treated with an ACE inhibitor receiving the last dose of that agent within 36 hours prior to randomization, a valsartan bridge for one day will be administered in a blinded manner prior to initiating the LCZ696 treatment. To achieve this, those who are subsequently randomized to LCZ696 will receive two doses of valsartan in a blinded manner prior to beginning double-blind LCZ696 treatment. Patients randomized to ramipril will immediately start on double-blind ramipril without valsartan bridging.

[Table 5-1](#) summarizes the study drug that will be taken during the treatment epoch.

Table 5-1 Study drug dispensed during the treatment epoch by study visit

Study visit ^c	Dose level	LCZ696	Ramipril	Valsartan ^b
101	1 ^a	50 mg or matching placebo b.i.d.	1.25 mg or matching placebo b.i.d.	40 mg or matching placebo b.i.d.
101 ^a /102	2	100 mg or matching placebo b.i.d.	2.5 mg or matching placebo b.i.d.	80 mg or matching placebo b.i.d.
103	3	200 mg or matching placebo b.i.d.	5 mg or matching placebo b.i.d.	

^a At Investigator's discretion, dose level 2 can be administered at Visit 101 for the [ACE inhibitor/ARB: Yes] patients.

^b For patients who were previously treated with ACE inhibitor receiving the last dose within 36 hours prior to randomization;

If randomized to LCZ696, they will receive a valsartan bridging for one day before beginning the double-blind LCZ696 treatment.

- Two doses of blinded valsartan dose level V1 (valsartan 40 mg) or dose level V2 (valsartan 80 mg) will be available at Visit 101.
- At investigator's discretion dose level V1 or V2 can be administered for one day followed by active LCZ696; these patients will also receive ramipril matching placebo from Visit 101 onwards.

If randomized to ramipril, they will receive active ramipril, and two doses of valsartan matching placebo for one day followed by active ramipril and LCZ696 matching placebo.

^c If the study drug is up-titrated during the index hospitalization, increase to the next dose level can occur prior to next study visit if tolerable but should be no early than 24 hours; slower up-titration will also be permitted if necessary to manage patient safety and tolerability.

Patients will be instructed to take their morning study drug doses at approximately 08:00 (8 AM) and their evening study drug dose at approximately 20:00 (8 PM). The study drugs should be taken with water, with or without food. If the patient misses taking any study drug dose, he/she should take it as soon as possible, unless it is almost time for the following scheduled dose. In this case, the patient should skip the missed dose and return back to his/her regular study drug administration schedule.

All dosages prescribed and dispensed to the patient and all dose changes during the study must be recorded on the Dosage Administration Record case report form (CRF). All kits of study treatment assigned by the IRT will be recorded/databased in the IRT.

The investigator must promote compliance by instructing the patient to take the study treatment exactly as prescribed and by stating that compliance is necessary for the patient's safety and the validity of the study. The patient must also be instructed to contact the investigator if he/she is unable for any reason to take the study treatment as prescribed.

5.5.5 Permitted dose adjustments and interruptions of study treatment

For patients who are unable to tolerate the protocol-specified dosing scheme, dose level adjustments and/or temporary interruptions of study treatment are permitted in order to keep the patient on study drug. The following guidelines should be followed:

Every attempt should be made to maintain patients at the target study drug dose level throughout the trial. If the patient does not tolerate the target study drug dose level, the

investigator can, if appropriate, adjust concomitant background medications for co-morbid conditions to rectify the situation, and if necessary down titrate to the next lower study drug dose level. For hypotension or dizziness, consideration should be given to adjusting the dose of diuretic and/or concomitant antihypertensive agents (e.g., calcium channel blockers) and non-antihypertensive agents that lower blood pressure (BP) (e.g., nitrates). It is important to note that dose adjustment of disease-modifying background therapy, e.g., β blockers, or mineralocorticoid (aldosterone) antagonists is discouraged under these circumstances.

Adjustment of study drug dose level

If in the investigator's opinion down titration of study drug to a lower dose level is deemed necessary it should be done in accordance with the following instructions:

During the treatment epoch, down titration of the study drug at any time during the study based on the judgment of the investigator will be allowed according to the safety and tolerability criteria defined in [Appendix 4](#), and [Appendix 5](#). If down titration is necessary, the patient should be down titrated to the next lower study drug dose level in the titration scheme. The patient may continue receiving the lower dose level for a recommended period of 1 to 4 weeks before being re-challenged at the next higher dose level. For example, a patient who encounters tolerability problems at the target study drug dose level (i.e., dose level 3) should receive the study drug at dose level 2 for 1 to 4 weeks at the discretion of the investigator. Then, he/she should be re-challenged with up-titration back to dose level 3.

If the tolerability issues are not alleviated despite down titration by one dose level, the investigator may down titrate further to the next lower study drug dose level for 1 to 4 weeks, up to temporary discontinuation of the study drug. Again, once stable, the patient should be re-challenged with up titration to the next higher dose level every 1 to 4 weeks in an attempt to bring back the patient gradually to the target study drug dose level (i.e., dose level 3). The investigator may choose the next dose level for down- or up-titration according to his or her judgment. The IRT system should be contacted to register any changes in the patient's study drug dose level, including in cases of temporary and permanent discontinuation of the study drug, and to obtain the medication numbers of the study drug supplies required for the new study drug dose level. In some instances, according to the safety and tolerability criteria and the investigator's judgment, dose level 1 or 2 could be maintained if he/she considers that the patient's condition would not allow any further up titration to the target dose level of study drug (i.e., dose level 3). In this case, it would be acceptable to maintain the patient at dose level 1 or level 2, whichever is the higher and tolerated dose level by the patient.

These changes must be recorded on the Dosage Administration Record CRF.

Study drug restart after temporary treatment interruption

Study drug should be reintroduced in those patients who temporarily discontinue it as soon as medically justified in the opinion of the investigator. Once the investigator considers the patient's condition appropriate for receiving the study drug, the investigator should re-start the patient on the study drug at the most appropriate and allowable dose level per his/her medical judgment. If tolerated, the patient should be up-titrated one dose level every 1 to 4 weeks to the target dose level 3, as per the investigator's judgment. Should the patient not tolerate the re-start study drug dose level, he/she may be down titrated again (if appropriate) or

temporarily discontinue the study medication again and a new attempt to up titrate or reintroduce the study drug could be considered by the investigator as soon as medically justified in his/her judgment.

The use of an open-label ACE inhibitor, ARB, commercially available Entresto™ or a direct renin inhibitor is strictly prohibited while patient is taking study drug. However, if for any reason a patient off study drug has started open-label treatment with an ACE inhibitor or Entresto™, it must be discontinued ≥ 36 hours prior to restarting study drug. For patients off study drug treated with an ARB or a direct renin inhibitor it must be discontinued prior to re-initiation of study drug.

Reinitiation of study medications or any changes in concomitant medications must be recorded on the appropriate eCRFs.

In case of pregnancy discovered during the screening epoch, the patient will be withdrawn from the study immediately. In case of pregnancy discovered during the treatment epoch, the patient should be instructed to temporarily discontinue study drug immediately. Study drug intake should be resumed as soon as possible after the completion of the pregnancy and lactation period. Meanwhile, the patient should continue to attend scheduled study visits.

See [Section 7.6](#) for further details on pregnancies and reporting guidelines

5.5.6 Rescue medication

Guidance on handling hypotension and hyperkalemia are provided to investigators in [Appendix 4](#), and [Appendix 5](#), respectively. Patients may receive open-label ACE inhibitors, ARBs, commercially available Entresto™ or direct renin inhibitors during the study ONLY if the study drug has been temporarily or permanently discontinued ([Table 5-1](#)). If the patient is to be started on open-label ACE inhibitor or Entresto™, the study drug must be stopped ≥ 36 hours prior to initiating ACE inhibitor or Entresto™. If reinitiating study drug, the open-label ACE inhibitor or Entresto™ must be stopped ≥ 36 hours prior to resuming study drug. Open-label ARBs or a direct renin inhibitor must also be stopped prior to resuming study drug.

Use of rescue medication must be recorded on the Concomitant medications/Significant nondrug therapies CRF.

5.5.7 Concomitant medication

The investigator must instruct the patient to notify the study site about any new medications he/she takes after the patient was enrolled into the study. All medications, procedures and significant non-drug therapies (including physical therapy and blood transfusions) administered after the patient was enrolled into the study must be recorded in the concomitant medications eCRF.

Each concomitant drug must be individually assessed against all exclusion criteria/prohibited medication. If in doubt the investigator should contact the Novartis medical monitor before randomizing a patient or allowing a new medication to be started.

CV Medications

The patient should be on an optimal medical regimen of background medications to effectively treat the index MI event and comorbidities, such as hypertension, diabetes, dyslipidemia and atrial fibrillation, etc. Investigators should take into consideration the patient's risk factors, such as age and comorbidities, and make every effort to control a patient's BP, lipid and glucose levels in accordance with international and local treatment guidelines.

Medications known to raise potassium levels

Potassium-sparing diuretics, potassium supplements and any other medications known to raise potassium levels should be used with caution while the patient is receiving the study drug due to the increased possibility of occurrence of hyperkalemia. The investigator is encouraged to assess patients' potassium levels regularly, especially in those who are receiving these medications.

Phosphodiesterase-5 (PDE-5) inhibitors

PDE-5 inhibitors should be used with caution while the patient is receiving study medication due to the increased possibility of the occurrence of hypotension.

HMG-CoA reductase inhibitors

Caution is recommended when co-administering LCZ696 with atorvastatin or other statins because of the potential to raise its plasma level.

5.5.8 Prohibited medication

Use of the treatments displayed in [Table 5-2](#) is NOT allowed after the start of study drug due to safety reason, unless the actions specified are taken.

Table 5-2 Prohibited medication

Medication	Action taken
Any ACE inhibitor	Discontinue study drug. The open label ACE inhibitor must be stopped for ≥ 36 hours prior to re-initiation of study drug
Any ARB	Discontinue study drug. The open label ARB must be stopped prior to re-initiation of study drug
Any direct renin inhibitor	Discontinue study drug. The open label direct renin inhibitor must be stopped prior to re-initiation of study drug
Entresto™*	Discontinue study drug. The open label Entresto™ must be stopped for ≥ 36 hours prior to re-initiation of study drug

*Commercially available sacubitril/valsartan

The concomitant use of open-label ACE inhibitor, ARBs, commercially available Entresto™ or a direct renin inhibitor is strictly prohibited while the patient is receiving study drug. If the addition of an ACE inhibitor, ARB, Entresto™ or direct renin inhibitor is necessary, then study drug must be temporarily discontinued. If the patient is to be started on open-label ACE inhibitor or Entresto™, the study drug must be stopped ≥ 36 hours prior to initiating ACE

inhibitor or Entresto™. If study drug is to be re-started, the open-label ACE inhibitor or Entresto™ must also be stopped ≥ 36 hours prior to re-initiating study drug. ARBs or a direct renin inhibitor should be stopped prior to resuming study drug.

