Study drug/ treatment	Any single drug or combination of drugs administered to the patient as part of the required study procedures; includes investigational drug(s), placebo/comparator active drug run-ins or background therapy
Study Treatment Discontinuation (TD)	When the patient permanently stops taking study treatment prior to the defined study treatment completion date
Variable	A measured value or assessed response that is determined in specific assessments and used in data analysis to evaluate the drug being tested in the study
Withdrawal of consent (WoC)	Withdrawal of consent from the study is defined as when a patient does not want to participate in the study any longer, and does not want any further visits or assessments, and does not want any further study related contact, and does not allow analysis of already obtained biologic material, and does not allow any further collection of personal data

Amendment 4 (06-Aug-2020)

Amendment rationale

The purpose of this amendment is to add a second interim analysis in response to the COVID-19 pandemic with the stopping boundary for the primary endpoint at one-sided alpha of 0.005.

A novel coronavirus that had not previously been identified is causing clinical disease in humans (COVID-19). On 11-Mar-2020, the World Health Organization (WHO) characterized COVID-19 as a pandemic. As acknowledged by global Health Authorities in their guidance to the pharmaceutical industry, the COVID-19 pandemic has a global impact on the conduct of clinical trials of medicinal products. Challenges arising include at-risk patient populations, site closures, travel restrictions, shelter-in-place orders, interruptions to the supply chain for the investigational product, and other considerations if trial patients and site personnel become infected with COVID-19.

The significant impact of COVID-19 on the safety of patients and study personnel has greatly impacted study conduct. We have already observed marked increase in missed visits, treatment interruption due to drug supply issues related to the pandemic and substantial reduction of HF hospitalization and outpatient HF events. This observation is consistent with the published data which showed a greater than 50% reduction in the occurrence of HF hospitalization during the COVID-19 pandemic (Hall, et al. 2020), adding to other serious challenges on the conduct of the PARADISE-MI study.

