2.1.1 General definitions

Study treatment or drug

In future sections through this document, ‘study treatment’ or ‘study drug’ will be used to refer to investigational therapy assigned to a patient. Specifically, for the double-blind treatment phase, study treatment refers to LCZ696 or ramipril as assigned to a patient at randomization.

Screening epoch or screening period

Screening epoch or screening period is defined as the period starting from date of signed of informed consent until date of randomization or decision on randomization.

Randomized treatment phase

The randomized treatment phase begins at the time of randomization and ends with the last study drug intake or the death of the patient, whichever comes earlier. During the randomized treatment phase, patients will return for scheduled clinic visits. For all related safety analyses randomized treatment starts with the first intake of randomized, double-blind study drug. Temporary interruption of the study drug will not be counted as randomized treatment phase discontinuation.

Post-treatment follow-up phase

The post-treatment follow-up phase (usually after premature permanent study drug discontinuation) begins after last study drug intake + 1 day and ends on the date last seen (or vital status confirmed by indirect contact).

Double-blind period or double-blind treatment epoch

The double-blind period, also called the double-blind treatment epoch, is the combination of the randomized treatment phase and the post-treatment follow-up phase.

Baseline and study day

For analysis purpose, baseline value for all variables is defined to be the last results obtained at or prior to randomization date (or prior to 1st study drug intake for safety assessments). Most of variables will have their baseline at visit 101, unless otherwise specified. [REDACTED]

Study day of any assessment refers to the number of days to the assessment relative to randomization (day 1), or relative to the 1st study drug intake for safety assessments.

Unscheduled visit

Only for the analysis of safety laboratory evaluation will unscheduled measurements be taken into account. For efficacy evaluations, measurements from unscheduled visits will generally not be used, unless specifically specified.

On-treatment data for an efficacy endpoint

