The on-treatment data refers to any observation occurring while the patient is on-study medication or within 28 days inclusive of permanent treatment discontinuation excluding any observation occurring thereafter.

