An ‘on-treatment’ analysis ([Section 2.1.1](#)) will also be performed for the primary endpoint whereby events that occurred more than 28 days after permanent study treatment discontinuation will be excluded from the analysis. For patients without events before or at 28 days after treatment withdrawal, the censoring date will be the minimum of the date of permanent study treatment discontinuation + 28 days and the date of standard censoring for the endpoint.

The primary analysis will also be repeated for per-protocol set (PPS) for assessing robustness of results to significant protocol deviations leading to exclusion from FAS.

Sensitivity and supplementary analyses

1. If the study is stopped early for efficacy at the second interim analysis, or the study is terminated early by the sponsor due to prolonged COVID-19 impact, the following sensitivity and supplementary analyses will be performed:
 - (1) As a sensitivity analysis to the above proportional hazards analysis, treatment groups will be compared for the primary efficacy variable using a stratified log-rank test with STEMI/NSTEMI as a stratification factor, including CEC-confirmed primary endpoint events that occurred prior to 01-Mar-2020 (estimated start of COVID-19 impact globally).
 - (2) Analysis with adjustment of country instead of region in the primary analysis model as specified in [Section 2.5.2](#), using CEC-confirmed primary endpoint events that occurred prior to 01-Mar-2020.
 - (3) A supplementary analysis using the primary analysis model as specified in [Section 2.5.2](#), including all CEC-confirmed primary endpoint data accrued up to the end-of-study analysis cut-off.

2. If the study is not stopped at the second interim analysis and continues to the end, the following sensitivity and supplementary analyses will be performed:
 - (1) As a sensitivity analysis to the above proportional hazards analysis, treatment groups will be compared for the primary efficacy variable using a stratified log-rank test with STEMI/NSTEMI as a stratification factor, including all CEC-confirmed primary endpoint data accrued up to the end-of-study analysis cut-off.
 - (2) Hypothetical estimand approach (see Table 2-4 for the definition of the hypothetical estimand in a world without the COVID-19):

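### The supportive on-treatment analysis of the primary endpoint has no cut-off at the start of an open-label RAS inhibitor or Entresto, so events on those drugs during a temporary stop count as on randomized drug

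*Protocol*

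**What the plan says.** All references are to the current protocol (Amendment 4) and the current SAP.

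**The on-treatment rule.** SAP 2.5.4 states that "events that occurred more than 28 days after permanent study treatment discontinuation will be excluded from the analysis". Where no event has occurred by then, "the censoring date will be the minimum of the date of permanent study treatment discontinuation + 28 days and the date of standard censoring". Protocol 9.4.2 gives the same rule. Neither text mentions temporary interruption or the start of open-label therapy.

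**The general definition.** SAP 2.1.1 says: "The on-treatment data refers to any observation occurring while the patient is on-study medication or within 28 days inclusive of permanent treatment discontinuation". Under the randomized treatment phase, the same section adds: "Temporary interruption of the study drug will not be counted as randomized treatment phase discontinuation".

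**Discontinuation.** The protocol glossary defines study treatment discontinuation as "When the patient permanently stops taking study treatment prior to the defined study treatment completion date".

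**Open-label therapy.** Protocol 5.5.8 says: "If the addition of an ACE inhibitor, ARB, Entresto™ or direct renin inhibitor is necessary, then study drug must be temporarily discontinued". Section 5.5.6 allows open-label ACE inhibitor or ARB only while study drug is stopped, whether temporarily or permanently. Section 5.6.2 likewise lists use of any of these drugs as a reason for either kind of stop and allows restart. Section 5.5.5 describes restart after open-label use and sets no maximum length for an interruption.

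**The concern.** An on-treatment analysis is read as the effect while patients take the assigned drug. Here, a patient whose stop is recorded as temporary stays in the on-treatment risk set for as long as the stop lasts, even when taking another RAS inhibitor. A patient randomized to LCZ696 could be on an open-label ACE inhibitor, the comparator's class. A patient randomized to ramipril could be on open-label Entresto, the investigational drug. Events in that time would be credited to the randomized arm.

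The SAP already treats such switching as important elsewhere. SAP 2.6.5 censors ramipril patients at the start of open-label Entresto, but only for secondary endpoints (1), (3) and (5). The sample exclusion list in SAP Table 5-1 has no entry for open-label RAS inhibitor use, so the per-protocol analysis does not remove it either. What is at stake is how one supportive result is read, not the primary test.

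**Working it through.** **Step 1. Apply the rule to one course of events.** A patient stops study drug on day D, starts an open-label ARB soon after, and has a first primary event four months later.

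- Stop recorded as temporary: there is no permanent discontinuation date, so the only limit is standard censoring. The event is counted.
- Same stop recorded as permanent on day D: the cut-off is D + 28 days. The event is excluded.
- With a cut-off at open-label start: the patient is censored at the start of the ARB under either label.

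So under the present rule the handling depends on how the stop is labelled, not on what the patient is taking.

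**Step 2. Look for another rule that removes this time.**

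- SAP 2.6.5 (IPCW): ramipril arm only, Entresto only, secondary endpoints (1), (3) and (5) only.
- SAP 2.5.4, subject-specific COVID-19 censoring: this is a primary-endpoint analysis and it is triggered by, among other things, interruptions over 3 months, but only those due to COVID-19. It targets a different estimand.
- SAP 2.4.1 and 2.4.2: exposure excluding interruption days, and open-label drug use, are described but do not enter the on-treatment model.

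None of these adds an open-label term to the on-treatment analysis.

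**Step 3. Illustrate the size.** The documents give no share of events in such time, so the share is an assumption. Let s be the share of counted events that fall in open-label time during temporary stops. Take 0.81 as the on-drug hazard ratio (the design value in protocol 9.8.2) and assume 1.0 in that time. Averaging log hazard ratios with weights by events gives

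HR = exp[(1 − s) × ln 0.81 + s × ln 1.0] = 0.81^(1 − s)

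- s = 0.05: 0.81^0.95 = 0.819
- s = 0.10: 0.81^0.90 = 0.827
- s = 0.20: 0.81^0.80 = 0.845

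Weighting instead by share of at-risk time q, equal in both arms and with the same control hazard, HR = (1 − q) × 0.81 + q × 1.0 gives 0.820, 0.829 and 0.848 for q = 0.05, 0.10 and 0.20. The two approximations agree closely.

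For scale, if the analysis counted all 708 target events, 5% would be 708 × 0.05 ≈ 35 events and 20% would be 708 × 0.20 ≈ 142. The upper end is therefore a wide bound rather than an expectation.

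**Step 4. Check that the primary design is untouched.** The design figures reproduce. With 708 events and HR 0.81, power = Φ(√708/2 × |ln 0.81| − 1.960) = Φ(2.804 − 1.960) ≈ 80% at one-sided 2.5%, as stated. The primary analysis uses all follow-up regardless of treatment discontinuation, so the on-treatment rule does not enter it.

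**The case against.** The strongest reply has five parts.

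1. **Many open-label starts will already be cut.** Section 5.5.6 recommends an open-label ACE inhibitor or ARB when discontinuation is considered despite dose reduction or interruption, and 5.6.2 allows the stop to be permanent. Those cases end at + 28 days. If permanent stops are dated back to the last dose, interruptions that never resume are cut as well. This stands and narrows the point to stops recorded as temporary, which 5.5.5, 5.5.6 and 5.5.8 all foresee.

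2. **Much Entresto use will follow a primary event.** SAP 2.6.5 expects switching at the first symptomatic HF event. If that event is confirmed, it has already ended time-to-first follow-up for the primary endpoint. This also stands. What remains is open-label use for other reasons, or before any confirmed event.

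3. **The SAP states its convention on interruptions.** Because 2.1.1 says an interruption does not end the randomized treatment phase, being on study medication can be read as being within that phase, which makes 2.5.4 consistent with it. This stands as to plain interruptions. It does not address time on a different active drug.

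4. **Interruptions may be short, and the long COVID-19 ones are handled.** Section 5.5.5 works in steps of 1 to 4 weeks and urges early restart. The Amendment 4 rationale reports "treatment interruption due to drug supply issues related to the pandemic", but SAP 2.5.4 has a COVID-specific analysis that censors long interruptions. This is fair as to interruptions in general; neither argument supplies a rule for open-label drug.

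5. **Direction is not known.** A ramipril patient on an open-label ACE inhibitor, or an LCZ696 patient on open-label Entresto, may keep the assigned contrast. Stops may be prognostic or differ by arm. This stands, and the figures above are only illustrations.

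**Conclusion.** The on-treatment analysis lacks a cut-off at open-label start, and adding one is a cheap improvement. The conclusion rests on the wording of protocol 9.4.2 and SAP 2.5.4, and on protocol 5.5.6, 5.5.8 and 5.6.2 allowing open-label drug during a temporary stop of any length. The illustrative shift is from 0.81 to about 0.82–0.845 under an assumed share of 5% to 20% and an assumed hazard ratio of 1.0 in that time. The true size and direction are unknown.

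A reader might infer more than the documents support:

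- *That SAP 2.1.1 and 2.5.4 contradict each other.* They are ambiguous together. The sentence on temporary interruption in 2.1.1 allows a consistent reading.
- *That every patient needing open-label therapy is placed on a temporary stop.* Section 5.5.8 speaks of a temporary stop, but 5.6.2 covers both kinds.
- *That all interruption time should be removed.* That is a trade-off. Censoring at any gap over 28 days permanently drops patients who restart, and the gaps may be prognostic.
- *That the on-treatment hazard ratio is biased toward 1.* No figure in the documents establishes this.
- *That the primary result is at risk.* The primary test, alpha and power are unaffected.

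**What to change.** In SAP 2.5.4 and protocol 9.4.2, end on-treatment follow-up at the earliest of:

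- permanent study treatment discontinuation + 28 days;
- start of any open-label ACE inhibitor, ARB, direct renin inhibitor or Entresto, in either arm;
- the standard censoring date.

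Align the on-treatment definition in SAP 2.1.1 with this rule, and say there explicitly that interruption time without open-label drug counts as on-treatment, if that is the intention. Censoring at interruptions longer than 28 days should be at most an additional sensitivity display, not a replacement.

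**Cost.** Wording and a small amount of programming. Open-label drug dates are already collected (protocol 5.5.6 and 5.5.7), and SAP 2.6.5 already defines a censoring time at open-label Entresto start. There will be slightly fewer events, including some now counted in the 28 days after a permanent stop when open-label drug begins within that window. There will also be slightly more possibly informative censoring, in a supportive analysis only. The change concerns analysis rules; no change to clinical management is proposed.
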